4.1 Primary outcome measures

In the first part of the study (PUK-GHB01), plasma hormone levels, subjective effects assessed by questionnaires, and social cognition parameters assessed by specific computed test batteries, as well as brain activity assessed by electroencephalography (EEG) and functional magnet resonance imaging (fMRI) will serve as primary outcome measures. The results of the neuropsychological test battery performance will serve as longitudinal safety parameters to detect unexpected cognitive impairment after GHB intake. In the second part (PUK-GHB02), plasma hormone levels, GHB levels in plasma, urine, hair, and nails, sleep biomarkers such as brain-derived neurotrophic factor (BDNF), fragile x mental retardation protein (FMRP), IL-beta, IL-6, IL-10, TNF-alpha, CRP, IL-4, IL-18 und IFN-gamma, tryptophan, kynurenin, kynurenic acid, neopterin, malondialdehyd, qinolinsäure, IDO (indolamine-2,3-deoxygenase), substance P, and genetic markers, cognition, memory consolidation assessed by procedural and declarative memory tests, polysomnographic parameters, cerebral GHB-, GABA-, and Glu-concentrations in the ACC, Nacc, and amygdala, resting state connectivity, and measures of daytime sleepiness such as the Epworth Sleepiness

Scale (ESS), as well as subjective mood measures such as the Visual Analog Mood Scale (VAMS), and the Positive and Negative Affect Scale (PANAS) will serve as primary outcome measures.

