4.2 Design of the Experiments PUK-GHB01 and PUK-GHB02

4.2.1 PUK-GHB01: social cognition and hormones

Thirty-two male healthy subjects will be assessed with questionnaires (GHB Specific Questionnaire [GSQ], Sexual Arousal and Desire Questionnaire [SADI], Profile of Mood States [POMS], Visual Analog Scale [VAS]), tests of social cognition (Sexual Arousal Task [SAT], Multifaceted Empathy Test [MET], Social Gaze Test [SGT], Movie for the Assessment of Social Cognition [MASC]), neuropsychology (Cambridge Neuropsychological Automated Test Battery [CANTAB], Flanker Task, Verbal Memory Test [VLMT]), neuroeconomic tests (Reciprocity Task [RT], Social Value Orientation [SVO], Charity Donation [CD]), electroencephalography (EEG), functional magnet resonance imaging (fMRI) and neuroendocrine blood tests (oxytocin, 3,5-THP, THDOC, ACTH, prolaktin, testosterone, cortisol, progesterone, N-Arachidonoylethanolamin, 2-Arachidonoylglycerol, Palmitoylethanolamid, Arachidonic acid, Linoleboylethanolamid, Oleoylethanolaid, Stearoylethanolamid, prostaglandin E2 and GHB) after application of GHB (days 1+2 20 or 35 mg/kg p.o., days 3+4 35 mg/kg p.o. vs. placebo – cross over design). The neuropsychological and neuroeconomic test as well as the tests of social cognition have already been implemented in trials of the Experimental and Clinical Pharmacopsychology research group of the Psychiatric University Hospital Zurich. The neurocognitive test will be performed on a study computer of the experimental and clinical pharmacopsychology research group of the Psychiatric University Hospital Zurich. The fMRI experiments will be performed at the MR Center of the University Hospital of Psychiatry Zurich. The assessment will follow the Good Clinical Practice (GCP) guidelines. Both neurocognitive and neuroendocrine tests will be performed paralleled, under two different conditions (20 or 35 mg/kg GHB p.o. vs. placebo; t₀= GHB application) on two days spaced at least 1 week apart. Neurocognitive testing will be performed during the peak of subjective GHB effects (t+ 30 until t + 90). Blood tests for neuroendocrinologic measures will be taken six times (t-30 min, t₀, t + 20 min, t + 35 min, t + 65 min, t +95 min, t + 124 min and t + 180 min). A total amount of blood of 150 ml will be taken during each experiment. The complete assessment will last about five hours. The two fMRI sessions will start at least one week after the two first experimental days, and succeed with at least one week in between. Each session takes a time of 2.5 hours. Furthermore, one pre- and one post-test session will be performed for medical check-up.

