4.5 Blood and other biosamples

4.5.1 Procedure

Experiment I: Every study subject takes part in at least two experimental sessions (GHB vs. placebo). An amount of blood of 150 ml (6 samples) will be taken by the principal investigator through an intravenous catheter during each session. For both sessions, a total amount of blood of 300 ml will be taken.

Experiment II: Every study subject takes part in four experimental sessions (2 x GHB vs. placebo), plus one preceding screening-night and one adaptation night anterior to each experimental night. A total amount of blood of 250 ml (18 samples, see 6.2) will be taken by a medical professional or a study nurse through an intravenous catheter during each session. Each sample will be tested for the quantities of the plasma markers IL-beta, IL-6, IL-10, TNF-alpha, CRP, IL-4, IL-18 und IFN-gamma, tryptophan, kynurenin, kynureninic

acid, neopterin, malondialdehyd, qinolinsäure, IDO (indolamine-2,3-deoxygenase) and substance P cortisol, progesterone, GHB, BDNF, FMRP, genetic markers, and prolactin. Moreover, other biosamples will be taken as follows: five hair samples (T0: before testing, T1: 2 days post-experimental night I, T2: seven days post-experimental night I, T3: two days post-experimental night II, T4: six weeks post-experimental night I, T5: before experimental night III, T6: the day after experimental night III, T7: the day after experimental night III), seven sweat samples (one sweat patch per night), four urine samples (after every adaptation and experimental night), nine nail samples (weekly nail clipping).

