4.7.2 Blinding procedure

Blinding will occur through a clinical staff member not involved otherwise in the study. This person will randomly abstract GHB (Xyrem) or placebo (0.9% saline solution) for each subject and put it into a plastic cup with 150 ml standard orange juice using a ml-syringe. In the first experiment (SocCog) sixteen subjects will receive 20 mg/kg and sixteen subjects 35 mg/kg GHB on one occasion and placebo on the other. For the MR-sessions, the same thirty-two subjects will receive 35 mg/kg GHB in one, placebo in the other session in a double-blind, randomized manner. In the second experiment 20 subjects will receive 50 mg/kg GHB on two occasions and placebo on two others. The information about the weight of the subject is transmitted anterior to this procedure. The cup is labeled with the study-code and will be kept back until the end of the study. When the cup is filled, it will be given to the principal investigator, who hands it out to the subject. The subject drinks the whole content and returns the empty cup to the principal investigator.

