7.1 Safety measures

Experiment	Method	Time (related to GHB application)
PUK-GHB01 days1+2	Blood pressure/pulse (BP/P)	t -40, 0, +20, +40, +120 min
PUK-GHB02	Supervision, EEG-Measures	see Flow Chart 6.2

Table 5 Safety measures: methods and time of testing

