8.3 Statistical analyses

We will use repeated measurements ANOVA for all dependent variables in both experiments.

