8.5 Drop outs

Drop outs will be excluded from the study.

9 Study specific precautions and obligations

9.1 Specific precautions.

For the study participants it is not allowed to use any illegal drugs during or seven days prior to the experiments. Participants should abstain from alcohol at least 48 h hours. Furthermore, it is not allowed to drive motor vehicles or to use machines subsequent to the experiments.

10 Investigators obligation

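### The drop-out rule in 8.5 is not limited to efficacy, so a dosed man who leaves PUK-GHB01 can lose a completed post-dose CANTAB from the cognitive safety check

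*Combined protocol and SAP*

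**What the plan says.** - Section 8.5, in full: "Drop outs will be excluded from the study". No definition of a drop-out follows, and nothing is said about data already collected.
- Section 8.3: "We will use repeated measurements ANOVA for all dependent variables in both experiments". Section 8 gives no other method and no analysis sets.
- Section 4.1, on the PUK-GHB01 neuropsychological battery: its results "will serve as longitudinal safety parameters to detect unexpected cognitive impairment after GHB intake". Section 4.3.1 identifies CANTAB as such a battery.
- Table 4 (6.1) lists CANTAB 1 at t -40 min and CANTAB 2 at t >24 h, under days 1+2 only. Table 5 (7.1) puts blood pressure and pulse at five times, also on days 1+2 only.
- Section 4.2.1: "The two fMRI sessions will start at least one week after the two first experimental days", with at least a further week between those two sessions.
- Section 4.5.1, Experiment I: "Every study subject takes part in at least two experimental sessions (GHB vs. placebo").
- Section 4.7.2: on days 1+2, "sixteen subjects will receive 20 mg/kg and sixteen subjects 35 mg/kg GHB on one occasion and placebo on the other". For the MR sessions, "the same thirty-two subjects will receive 35 mg/kg GHB in one, placebo in the other session".
- Section 10.2 sends serious adverse events and serious drug reactions to the regulator and the ethics commission. Section 12.4 has adverse events and vital signs recorded on the CRF. Section 10.1 is a general commitment to GCP.

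**The concern.** Section 4.2.1 lets a session be stopped for a threat to health or at the subject's wish, so leaving can be related to tolerability. A man who feels impaired or unwell after a dose is the man a cognitive safety check exists to find, and he is also more likely than others to leave. If his completed post-dose test is then removed, the check loses the result it was set up to catch. Because the rule has no efficacy limit and the plan has no all-dosed set, a reader of the results could not tell whether this had happened.

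**Working it through.** **Step 1. Does the narrow reading protect safety data?** Take 8.5 as a complete-case rule for 8.3. Section 8.3 covers every dependent variable, and 4.1 declares the neuropsychological battery a safety parameter. The narrow reading therefore still removes a drop-out from a safety measure.

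**Step 2. Who has something to lose?** Assume one CANTAB pair per session on days 1+2.
- Leaves before his first CANTAB 2: he has no post-dose value, so 8.5 costs nothing here.
- Leaves after his first CANTAB 2 but before completing the second session: he has one post-dose value, which is dropped.
- Leaves after day 2 and its CANTAB 2: he has both post-dose values and all 5 x 2 = 10 scheduled blood pressure/pulse readings. At least 1 + 1 = 2 weeks still remain to day 4. Whether he counts as a drop-out is not stated.

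If CANTAB 2 is instead a single test after both sessions, the second case has nothing to lose and only the third remains.

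**Step 3. What one exclusion does to an event rate.** The documents give no leaving rate, so this is an illustration only: one excluded man has the only event in his condition. Denominators are from 4.7.2; intervals are exact two-sided 95% (Clopper-Pearson). With no events the upper limit is 1 - 0.025^(1/n); for example 1 - 0.025^(1/15) = 21.8%.

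| Condition | All dosed men | After exclusion |
|---|---|---|
| 20 mg/kg, days 1+2 | 1/16 = 6.3% (0.2-30.2%) | 0/15, upper limit 21.8% |
| 35 mg/kg, days 3+4 | 1/32 = 3.1% (0.1-16.2%) | 0/31, upper limit 11.2% |
| 50 mg/kg, one pair of nights | 1/20 = 5.0% (0.1-24.9%) | 0/19, upper limit 17.6% |

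**Step 4. Direction.** The 20 mg/kg group has 16 GHB sessions and its own 16 placebo sessions.
- Event on GHB: 1/16 - 0 = +6.3 points becomes 0, a shift of -6.3.
- Event on placebo: 0 - 1/16 = -6.3 points becomes 0, a shift of +6.3.

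The two cases are symmetric. Setting the group against all 32 placebo sessions of days 1+2 would give only 1/32 = 3.1 points for a placebo event, but half of those sessions belong to the 35 mg/kg men.

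**Step 5. Precision.** A paired t test with the noncentral t distribution reproduces the sample size in 8.2: at d = 0.7 and two-sided 5%, power is 0.799 for n = 18 and 0.822 for n = 19, hence 19. By the same method, the effect detectable with 80% power goes from d = 0.511 (n = 32) to 0.520 (n = 31), or from 0.749 (n = 16) to 0.778 (n = 15). Losing one man costs little precision. What matters is which man is lost.

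**The case against.** The strongest reply is that 8.5 stands under Statistics and is simply a complete-case rule for the ANOVA. That is its most natural reading, but Step 1 shows that it does not rescue the cognitive safety measure.

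A related reply is that a man with only one condition has no within-subject contrast, so a standard repeated-measures ANOVA would omit him whatever 8.5 said. This is correct. It means that rewording 8.5 is not enough on its own: his CANTAB needs a place outside the ANOVA.

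Three further replies narrow the point.
- No adverse-event table is planned, so there is no specified summary for 8.5 to distort. The adverse-event part rests on the literal wording and on whatever safety report is eventually written.
- The pairing of CANTAB with each session is inferred from a table that did not survive extraction cleanly; 4.2.1 also mentions a single post-test session, and the chart of session order is not shown.
- A reader might infer that a man who stops after day 2 forfeits complete data. The documents lean the other way: 4.5.1 sets a minimum of two sessions, and 4.2.1 pays the fMRI sessions separately, with an extra 100 CHF. He is probably not a drop-out, though no text says so.

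A reader might also infer that serious events could vanish or that records are destroyed. Sections 10.2 and 12.4 rule that out. They govern notification and recording, however, and do not keep a drop-out's cognitive results or non-serious events in the reported findings.

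**Conclusion.** The point holds as a minor one. Section 8.5, applied as written, can remove completed post-dose cognitive safety data from dosed men in PUK-GHB01; this rests on one CANTAB pair per session. On the literal reading it would also leave non-serious adverse events out of any safety report, in either experiment. The cognitive part does not extend to PUK-GHB02, where 4.1 treats cognition as an outcome and not as a safety parameter.

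Size and direction cannot be derived. A reader might infer that the rule flatters GHB, or that it could halve a reported event rate. The first fails because excluding a man with a placebo event makes GHB look worse by the same amount. The second needs an assumed share of affected men who leave, and the documents give none. The illustrative shift is 6.3 points either way for one man in a group of 16, well inside the exact intervals.

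**What to change.** Replace 8.5 with:

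> Drop-outs are excluded only from the repeated-measures ANOVA of efficacy outcomes. Every man who receives at least one dose of GHB or placebo stays in the safety summary, with his adverse events, vital signs and any completed post-dose CANTAB. Each withdrawal is listed with its reason and the condition of the last session. A man who completes days 1+2 but not days 3+4 keeps his days 1+2 data in all analyses.

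In the safety summary, report CANTAB 2 minus CANTAB 1 by condition for every session that has both values, so that a man with one session is counted. State in Table 4 whether the pair is taken in each session. If adverse events are tabulated, compare each GHB dose group with the same men's placebo sessions.

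The cost is a little more reporting work on data already collected, with no added visits or procedures. The tolerability results may change slightly, in either direction.

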10.1 GCP and law

The study will be conducted according to the protocol, Good Clinical Practice (GCP) guidelines and the law.

10.2 Serious adverse events (SAE) and changes of protocol

Serious adverse events (SAE), serious adverse drug reactions (Serious ADR) as well as changes in the protocol will be communicated to Swissmedic and the ethical commission.

10.3 Insurance

In case of any unforeseen health problems the study participants are covered by insurance (Zürich Versicherungs-Gesellschaft Nr. 9.723.614), medical treatment will be provided free of charge. The legal venue is Zurich.

11 Ethical considerations

11.1 Risk-benefit analysis

We aim to perform a pharmacological challenge study with GHB under two circumscribed conditions (wake and sleep) with two single expositions to the substance compared to placebo for each subject in the first experiment and two single expositions in the second experiment. GHB is internationally approved for the

27/32

treatment of narcolepsy and was shown to have a favorable safety profile both for therapeutic and experimental use (Kantrowitz et al., 2009). However, concern has been raised regarding toxicity and possible dependency from GHB and the possibility of its misuse or abuse (Nicholson and Balster, 2001). The risk of acute toxicity using the herein proposed doses is extremely low, as multicenter studies and post marketing surveillance for GHB (Xyrem) suggested a very low incidence of unexpected side effects even in long term use (Wang et al., 2009). Residual toxicity of GHB is very small as endogenous and exogenous GHB is rapidly and completely converted into CO₂ and H₂O through the tricarboxylic acid cycle (Krebs cycle) (Maitre, 1997). Regarding the often cited concern about the potential addictive effect of GHB, animal studies showed a relatively low reinforcing effect compared to barbiturates and benzodiazepines. GHB and its precursors 1,4-butanediol (BDL) and gamma-butyrolactone (GBL) were not able to substitute for pentobarbital, methohexital, midazolam, diazepam or flumazenil in rhesus monkeys. Self-administration was lower than with these substances and the total maintained self-administration was marginally above saline levels (McMahon et al., 2003). In humans, a clear differentiation has to be done between illicit uncontrolled and medically supervised use of the substance. Cases of physical dependence have been reported in recreational illicit GHB users, but exact statistical analysis remains difficult as the estimated number of unreported non-dependent users is not known (Miotto et al., 2001, Degenhardt et al., 2002). Compared to this, reported rates of substance dependency as defined by DSM-IV criteria and physical dependency respectively, after the use of therapeutically applied GHB are one case for every 6500 patients treated and one case for every 3300 patients treated, or approximately 0.015% and 0.031% (Wang et al., 2009). These data apply to controlled daily use over periods up to 30 years. Thus, the cumulative post marketing and clinical experience indicates a very low risk of abuse/misuse of therapeutically applied GHB. Given that this study implies only a maximum of four exposures to the drug in doses, which are lower or equivalent to therapeutic doses, and that the expected results are important for the understanding of the complex relationships between hormonal, cerebral, cognitive and behavioral functions in humans, the risk-benefit analysis clearly suggests a benefit for conducting both trials.

12 Quality control

12.1 Data access

Access to the original data is guaranteed to the members of the ethical commission and the authorities, inspections may take place.

12.2 Privacy

The participants will remain anonymous; no personal identifying information will be published, passed on to authorities or elsewhere. Electronic data will be password protected; paper data will be stored in a key locker.

12.3 Monitoring

Trial monitoring will occur on-site before, during and after the trial. [name] (see page 2) will act as monitor and ensure that the trial is conducted and documented properly. A written report will be submitted to the sponsor after each trial-site visit by the monitor. The monitoring agreement consists of the monitoring requirements according to the Guidelines of Good Clinical Practice (GCP, 1996, Chapter 5.18 Pp.: 26-28; see Anlage 8m and 8n, "Monitoring-Checklisten"). The monitor has direct access to the complete source data, with exception of the subject identification list.

